# 11. Urgent Safety Measures

The Clinical Trials Regulations make provision for the Sponsor and PIs to take appropriate Urgent Safety Measures (USMs) to protect a research participant from an immediate hazard to their health and safety. This measure can be taken before seeking approval from the Research Ethics Committee (REC).

If any urgent safety measures are taken, BCTU shall immediately, and in any event no later than 3 days from the date the measures are taken, give written notice to the REC of the measures taken and the reason why they have been taken.

## 12. DATA HANDLING AND RECORD KEEPING

#### 12.1. Source Data

Source data is defined as all information in original records and certified copies of original records of clinical findings, observations, or other activities in a clinical trial necessary for the reconstruction and evaluation of the trial. In order to allow for the accurate reconstruction of the trial and clinical management of the participants, source data will be accessible and maintained.

**F4S-2** is a trial which is using an App, and therefore some of the data, e.g., App usage, will be generated in the App from participant's direct input

**Table 3: Source Data** 

Data	Source	
Participant Reported Outcomes (including Health Economics data).	The original completed participant reported outcome booklet is the source documentation. These will be either be stored with the participant's trial record:  • at site, where the questionnaires have been administered by site in clinic  • at Trial Office, where the questionnaires have been posted by and returned to the Trial Office	
Clinical event data	The original clinical annotation is the source document.  This may be found on clinical correspondence, or electronic or paper participant records. Clinical data reported by the participant, either in or out of clinic (e.g., phone calls), must be documented in the source documents.	
Data uploaded to the F4S App	User usage and engagement data will be transferred to BCTU servers in the form of JSON files and will be the source documentation.	
Recruitment	The original record of the randomisation is the source. It is held on BCTU servers as part of the randomisation and data entry system.	
Withdrawal	Where a participant expresses a wish to change their level of participation, the conversation must be recorded in the medical records, and this will constitute the source data.	

# 12.2. Case Report Form Completion

An electronic case report form (eCRF) should be completed for each individual participant, and these will be electronic with the exception of the participant completed questionnaires.

The eCRFs will include, but will not be limited to, the forms listed in Table 4.

Table 4: List of trial specific CRFs

Form Name	Schedule for submission	
Randomisation CRF	At the point of randomisation	
Baseline CRFs, including participant reported outcomes	At the point of randomisation	

Follow-up CRFs, including participant reported outcomes	As soon as possible after each follow-up assessment time point		
Trial withdrawal/Change of status Form	At the point of becoming aware of withdrawal/change of status or death		

If data has not been provided within two weeks of the submission schedule detailed in the above table, a reminder email will be sent to sites. If data is consistently not provided, the Trial Office will directly contact the site to ascertain the reason for the delay. This may also be escalated to the site's senior management and can trigger a monitoring visit.

In all cases it remains the responsibility of the PI to ensure that the eCRF has been completed correctly and that the data is accurate. This will be evidenced by the electronic signature of the PI or delegate(s)The **F4S-2 Site Signature & Delegation Log** will identify all those personnel with responsibilities for data collection. The delegated staff completing the CRF should ensure the accuracy, completeness and timeliness of the data reported. This will be evidenced by signing and dating the eCRF.

Data reported on eCRFs will be consistent with the source data and any discrepancies will be explained. All missing and ambiguous data will be queried. Staff delegated to complete eCRFs will be trained to adhere to trial specific working instructions on CRF Completion.

The following guidance applies to data:

- Rounding conventions rounding should be to the nearest whole number: If the number you are rounding is followed by 5, 6, 7, 8, or 9, round the number up. (e.g. 3.8 rounded to the nearest whole number is 4). If the number you are rounding is followed by 1, 2, 3 or 4, round the number down. (e.g. 3.4 rounded to the nearest whole number is 3).
- Trial-specific interpretation of data fields where guidance is needed additional information will be supplied.
- Entry requirements for concomitant medications (generic or brand names) generic names should be used where possible.
- Repeat tests the data used to inform clinical decisions should always be supplied. If a test is repeated it is either to confirm or clarify a previous reading. Confirmatory tests should use the original test values.
- Protocol and Good Clinical Practice (GCP) non-compliances should be reported to the Trial Office when become aware.

# 12.3. Participant completed Questionnaires

A list of participant-completed forms can be found in Table 5.

Table 5: Participants completed questionnaires included in the participant booklets

Name of questionnaires	
IPAQ-E	
PG-SGA	
EORTC-QLC-C30	
EORTC-QLC-LC29	
EQ-5D-5L	
Hospital Anxiety and Depression Scale (HADS)	
Subjective Vitality Scale (SVS)	
EQ 5D VAS	
Health Resource Usage Questionnaire	
Motivational Processes (Intervention only)	
Shortened scales of behavioural change (Intervention only)	

The participant questionnaires listed above will be combined into booklets and completed by the participants on paper either in clinic or via postal paper questionnaire.

### For questionnaires completed:

In clinic – questionnaires will be administered by sites in clinic at baseline, day of surgery and 30 day follow up visit. The research team will oversee completion and provide support if necessary. Where support is provided, the questions should be read to the participant verbatim and responses must not be led by the person assisting the form completion. Participant should be encouraged to respond to all questions but can refuse to answer any or all of the questions should they wish. Checks for missing data and completeness should be done by the researcher before the participant leaves the visit. Where questions are unanswered, the researcher should clarify whether the participant chooses not to answer or simply missed in error. Should they choose not to answer, this should be marked clearly on the paper and database.

**Via post** - questionnaires will be posted to the participants by the Trial Office ahead of each scheduled follow-up time point, except baseline, day of surgery and 30 day follow up visit. A return freepost envelop will included for participants to return the completed questionnaires back to the Trial Office. Questionnaires should generally be completed by the participant alone but physical assistance in completing the form can be given by the participant's friends and relatives where appropriate. In such circumstances, questions are to be read to the participant verbatim and responses must not be led by the person assisting

with the form completion. This requirement must be made clear when the participant's friends and relatives are providing the assistance.

Upon receipt of a completed questionnaire, the Trial Office will check for unanswered questions or ambiguous answers. When completed questionnaires have not been returned by participants one reminder will be sent to them after the 3 month and 6 months' time points.

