#### 8.2. Main Trial Outcomes

### 8.2.1 Primary Outcomes

- Patient-reported quality of physical function scale recovery (using the EORTC-QLQ-C30) at 30 days after surgery
- Surgical complications (using the Comprehensive Complication Index (CCI)) at 30 days after surgery

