# 8.2.4 Patient Reported Outcomes

Patient reported outcomes will be collected via paper booklets (unless stated) administered either during routine hospital visits or posted direct to the participants, they will consist of:

- Patient-reported quality of life (using the EORTC-QLQ-C30, LC 29)
- Mental health/well-being (using the HADS)
- Symptom score (using a VAS) (intervention only obtained from the F4S App)

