## 30 days post-Surgery

- Assessment of complications post hospital discharge (Comprehensive Complication Index (CCI))
- Nutritional assessment including weight (PG-SGA SF)
- Physical tests Muscle strength hand grip, ISWT and sit to stand test
- Participant completed questionnaires to include EORTC-QLC-C30 & LC29, EQ-5D-5L,
   HADS
- Post-operative questions assessing usual care
- Post-operative Nutritional input assessment (drinks and dietitian)
- Health resource usage questionnaire

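### The day-30 QLQ-C30, a primary outcome, has no stated fallback or participant reminder, and the day-30 CCI review may take place before day 30

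*Protocol*

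**What the plan says.** Section 8.2.1 names two primary outcomes: "Patient-reported quality of physical function scale recovery (using the EORTC-QLQ-C30) at 30 days after surgery" and "Surgical complications (using the Comprehensive Complication Index (CCI)) at 30 days after surgery".

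**Questionnaire.** Section 8.2.4 says in general that patient-reported outcomes are "administered either during routine hospital visits or posted direct to the participants", without naming time points. Section 12.3 assigns them: "questionnaires will be administered by sites in clinic at baseline, day of surgery and 30 day follow up visit". The Trial Office posts the rest "ahead of each scheduled follow-up time point, except baseline, day of surgery and 30 day follow up visit". For questionnaires not returned, "one reminder will be sent to them after the 3 month and 6 months' time points". Under Section 15.2.4, participants with missing primary outcome data are left out of the primary analysis at first, and the protocol itself calls this a risk of bias.

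**Complications.** Section 9 records in-hospital complications at discharge and post-discharge complications at the 30-day visit. Table 2 puts a window of plus or minus 7 days on the 30-day column, which includes the CCI row. (The table header is broken in the text available; the window is matched by column order.) Section 10 says that events are collected up to 30 days after surgery, and ties note review to two time points: discharge and the 30-day follow-up.

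**The concern.** Of the questionnaire time points after discharge, the one that carries a primary outcome has the least protection against non-response. Someone who is readmitted, unwell or far from the hospital on the visit date has no stated other way to give the score. The visit also includes a shuttle walk, a grip test and a sit-to-stand test, which an unwell patient may prefer to avoid. Section 1.1 quotes complications in up to 45% of patients and readmission in 13%, so this group need not be small. If those who miss the visit function worse, the complete-case analysis describes a healthier subset. If the two arms differ in how many are missing, or in how much worse the missing are, the treatment comparison is biased. Under Section 7.8 the same booklet also counts towards adherence in both arms.

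The second issue is one of observation time. An outcome that accumulates to day 30 cannot be fully ascertained on day 23. An analysis plan can later discard events dated after day 30. It cannot recover events on days 24 to 30 that nobody looked for.

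**Working it through.** **1. Follow-up routes after discharge, from Section 12.3**

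| Time point | Route | Participant reminder |
|---|---|---|
| 14 days | Post | None stated |
| 30 days (primary) | Clinic; excluded from post | None stated |
| 3 months | Post | One |
| 6 months | Post | One |

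Day 30 is the only row with neither post nor reminder.

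**2. The plan's own sample sizes**

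Section 15.1 uses two-sided alpha 0.025, 90% power and 20% attrition. The formula is n per arm = 2 × (2.241 + 1.282)² × SD² / d².

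- CCI, SD 19, d = 5: 2 × 12.41 × 361 / 25 gives 359; 359 / 0.8 gives 449. The t-based version gives 360 and 450. The plan states 451.
- Physical function, SD 20, correlation 0.6: adjusted SD = 20 × √(1 − 0.36) = 16; 2 × 12.41 × 256 / 25 gives 255; 255 / 0.8 gives 319 (t-based: 256 and 320). The plan states 320.

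Both reproduce and are not in dispute.

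**3. Is power the problem?**

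Power for physical function with 451 randomised per arm; only the 20% comes from the protocol:

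| Missing at day 30 | Analysed per arm | Power |
|---|---|---|
| 20% | 361 | 97.5% |
| 30% | 316 | 95.4% |
| 40% | 271 | 91.8% |

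Power survives heavy loss, because the trial is sized for the CCI. What remains is bias, which the 20% allowance does not address.

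**4. Size of a possible bias in physical function**

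In one arm, let m be the fraction missing and D the observed mean minus the missing mean. The full-cohort mean is (1 − m) × observed + m × missing, so the observed mean exceeds it by m × D. The bias in the treatment difference is the difference in m × D between arms. With the same D in both arms, this is D × (difference in m). All values below are assumptions.

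- D = 10, rates 5 points apart: 0.05 × 10 = 0.5 points, or 0.5 / 5 = 10% of the target difference.
- D = 15, rates 10 points apart: 0.10 × 15 = 1.5 points, or 30%.
- Equal rates and equal D: 0.
- Equal rates of 20% but D of 15 in one arm and 10 in the other: 0.20 × (15 − 10) = 1.0 point.

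**5. Observation time for the CCI**

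The window runs from 30 − 7 = day 23 to 30 + 7 = day 37. A review on day 23 leaves days 24 to 30 unseen: 7 of 30 days. The protocol does not give the timing of complications, so the share of the CCI effect in that week is unknown. If a share f of the 5-point difference were lost overall and the SD stayed at 19, power with 361 per arm would be:

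| f | Remaining difference | Power |
|---|---|---|
| 0 | 5.00 | 90.2% |
| 5% | 4.75 | 86.8% |
| 10% | 4.50 | 82.7% |
| 20% | 4.00 | 72.1% |

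If the mean difference and SD shrank in proportion, power would stay at 90.2%.

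**The case against.** Clinic completion is a defensible choice at the key time point: Section 12.3 has staff oversee completion and check for blanks before the participant leaves. The plus-7-day margin leaves room to rebook. The text excludes routine posting ahead of the 30-day visit and does not forbid posting after a missed one. Completion of the day-30 questionnaires in each arm is a pilot progression criterion, with Go at 80% or more. Section 15.2.4 acknowledges the bias and plans multiple imputation as a sensitivity analysis. All of this is correct. It reduces the risk but does not supply the missing step: nobody is told to pursue an uncompleted day-30 booklet. Imputation by chained equations in its standard form assumes missingness at random, so it does not by itself correct informative loss.

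A reader might infer several stronger things that the protocol does not support:

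- **That the CCI is lost with a missed visit.** The gap in post and reminders concerns the questionnaire. The CCI also has the discharge assessment and note review, and sites are reminded about overdue data (Sections 12.2 and 12.4).
- **That the CCI as defined runs to the visit date.** The outcome is defined at 30 days, and nothing says that events on days 31 to 37 count. The gap is narrower: nothing says how days 24 to 30 are covered after an early visit, since note review is tied to the same time point.
- **That DAH30 is closed at this visit.** Neither Section 9 nor Table 2 lists DAH30 there.
- **That loss is selective or differs by arm.** This is plausible in an open-label trial, but it is not shown.

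**Conclusion.** The point holds in two limited parts. First, the day-30 QLQ-C30 has no stated fallback and no participant reminder, although those without it leave the primary analysis. The protocol thus protects the 3- and 6-month questionnaires better than the primary one. Second, an in-window complication review can take place up to 7 days before the outcome period ends, with no stated later check.

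Neither part shows that bias will occur. The 0.5 to 1.5 points for physical function rest wholly on assumed attendance differences and assumed score gaps. The CCI power figures rest on an assumed share of late events and range from no loss to a fall to 72.1%. The sample size stands. The case for change is that the weakness lies in data collection at the primary time point, cannot be fully repaired in analysis, and is cheap to close.

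**What to change.** **Section 12.3.** If the day-30 booklet is not completed in clinic, the Trial Office posts it with one reminder, for return within the plus-7-day window, and the mode of completion is recorded. The trigger should be the missed visit, or day 30 if no visit remains booked within the window; a visit missed near day 37 would leave little time for post.

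**Table 2 and Section 9.** Complete the CCI review on or after day 30, by note review if the clinic visit was earlier. Count only events dated up to day 30, and state the same cut-off for DAH30.

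**Cost.** A few extra postings through a route that the Trial Office already runs, event dates on the complication form, and a second look at the notes for participants seen before day 30. The main drawback is some mixing of clinic and postal completion in a primary patient-reported outcome. Recording the mode allows a sensitivity analysis, and the alternative for these participants is no score at all.

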# 12.4. Data Management

Processes will be employed to facilitate the accuracy and completeness of the data included in the final report. These processes will be detailed in the trial specific Data Management Plan (DMP) and include the processes of data entry and data queries.

Data entry will be completed by sites via a BCTU-managed trial database, however, questionnaires returned to the Trial Office will be entered by a member of the trial team at the Trial Office via the same trial database. The data capture system will conduct automatic range checks for specific data values to ensure high levels of data quality. Queries will be raised using data clarification forms (DCFs) via the trial database, with the expectation that these queries will be completed by the site (ideally) within 30 days of receipt. Overdue data entry and data queries will be requested on a monthly basis.

Self-evident corrections will be only be permitted when entering participant completed questionnaires to correct date fields, or complete logic tree's to allow entry of participant reported data, within the returned forms, by the Trial Office.

# 12.5. Data Security

The University of Birmingham has policies in place, which are designed to protect the security, accuracy, integrity and confidentiality of Personal Data.

The trial will be registered with the Data Protection Officer at UoB and will hold data in accordance with the Data Protection Act (2018 and subsequent amendments). BCTU has arrangements in place for the secure storage and processing of the trial data which comply with UoB policies.

The Trial Database System incorporates the following security countermeasures:

- Physical security measures: restricted access to the building, supervised onsite repairs and storages of back-up tapes/disks are stored in a fire-proof safe.
- Logical measures for access control and privilege management: including restricted accessibility, access controlled servers, separate controls of non-identifiable data.

• Network security measures: including site firewalls, antivirus software and separate secure network protected hosting.

- System Management: the System will be developed by the Programming Team at BCTU, and will be implemented and maintained by the Programming Team.
- System Design: the system will comprise of a database and a data entry application with firewalls, restricted access, encryption and role based security controls.
- Operational Processes: the data will be processed and stored within BCTU.
- System Audit: The System will benefit from the following internal/external audit arrangements:
  - Internal audit of the system
  - o Periodic IT risk assessment

Data Protection Registration: The UoB's Data Protection Registration number is Z6195856.In relation to the F4S App:

- Fit4S application suite is stored within a Microsoft Azure data centre in the United Kingdom. All data hosted and stored securely within the data centre.
- No personal information from participants is accessible or viewed by the Sub-Contractor from the F4S App.
- F4S admin module access is granted to site staff and it is stored in the database securely within the Microsoft Azure data centre in the United Kingdom.

## 12.6. Archiving

It is the responsibility of the PI to ensure all essential trial documentation and source documents (e.g. signed ICFs, ISFs, participants' hospital notes, CRFs etc.) at their site are securely retained for the contractual period. Archiving will be authorised by BCTU on behalf of UoB following submission of the end of trial report. No documents should be destroyed without prior approval from the BCTU Director or their delegate.

The Trial Master File (TMF) will be stored at BCTU for at least 3 years after the end of the study. Long-term offsite data archiving facilities will be considered for storage after this time; data will be stored securely and confidentially for 10 years. BCTU has standard processes for both hard copy and computer database legacy archiving.

# 13. QUALITY CONTROL AND QUALITY ASSURANCE

# 13.1. Site Set-up and Initiation

All local PIs will be asked to sign the necessary agreements, including a **F4S-2 Site Signature** and Delegation log, between the PI and BCTU and supply a current CV and GCP certificate. All members of the site research team are required to sign the Site Signature and Delegation Log, which details which tasks have been delegated to them by the PI. The Site Signature and Delegation Log should be kept up to date by the PI. It is the PI's responsibility to inform BCTU of any changes in the site research team.

Prior to commencing recruitment, each site will undergo a process of initiation, either a meeting or a tele/video conference, at which key members of the site research team are required to attend, covering aspects of the trial design, protocol procedures, adverse event reporting, collection and reporting of data and record keeping.

BCTU will provide each site with an ISF containing essential documentation, instructions, and other documentation required for the conduct of the trial. The PI or delegate is required to keep the ISF up to date throughout the trial.

# 13.2. Monitoring

The central and on-site monitoring requirements for this trial have been developed in conjunction with the trial specific Risk Assessment and are documented in the trial specific Monitoring Plan.

#### 13.2.1 Onsite Monitoring

For this trial, no onsite monitoring is planned due to the low risk of the intervention and nature of the outcome data. Should any monitoring activities be required they will be conducted by BCTU/ UoB staff. PIs and site research teams will allow the BCTU/UoB staff access to source documents as requested. Any monitoring activities will be reported to the Trial Office and any issues noted will be followed up to resolution.

## 13.2.2 Central Monitoring

BCTU will check received ICFs and CRFs for compliance with the protocol, data consistency, missing data and timing at a frequency and intensity as determined by the DMP. Sites will be sent DCFs requesting missing data or clarification of inconsistencies or discrepancies.

